A constrained longitudinal general linear model with unstructured covariance to take into account repeated measures on individuals over time will be used to estimate changes in the primary and secondary outcomes from T1 to T2 and from T1 to T3.³⁵ Often for trial analyses, intervention group and time are dummy coded indicator variables (i.e., levels 0 and 1) in model specification. Instead, given our factorial design, the main effects and interactions will be represented with effect coding (i.e., levels -1 and 1). In the scenario of balanced sample sizes across the factors, effect coding results in a model with independent coefficients.

Table 7

	Limitations identified in R34 pilot trial	Features planned for the mMT system in Aim 1
Engagement & personalization	
- Limited dynamic engagement (data display, notifications, reminders)- Limited interactivity and personalization of experience- Not ADA compliant	
1. Recommender system for:
- Sophisticated logic enabling stepped care- Robust symptom-responsive feedback- Visualization of use data2. ADA compliant features
Study mechanics	
- No screening system for post-discharge distress- Manual initiation of randomization	
3. Automated post-discharge screening & randomization system

Using the estimated model coefficients, we will first determine if any of the main effects indicate improvement of at least 2 points on the PHQ-9 at T2. Candidate components not reaching these benchmarks will be set to the “low” level of the component. We will then carefully examine the interactions, starting with those that include the largest main effect factor. Estimated means and plots will be used to explore the impact of the interactions and whether they are “synergistic” or “antagonistic.” The final “screened in” set of combinations (i.e., main effects and synergistic interactions indicating improvement of at least 2 points on the PHQ-9) will provide evidence of possible optimized intervention components.

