As the project centers around Aim 2 (RCT), we calculated power for the test of a main effect or factor interaction in a constrained longitudinal general linear model with unstructured covariance matrix via simulation. Based on LIFT pilot data, the baseline standard deviation of PHQ-9 was assumed to be 5.3 and the covariance between time points ranged from 3.9 to 11.5. We examined a range of sample sizes at T2, from 120 to 200 participants. 500 simulated datasets were simulated under the alternative model, with power calculated as the proportion of times the estimated coefficient was found to be statistically significant at $p < 0.05$. Results indicated that with 192 total patients at T2 (24 per experimental condition; 240 total at T1 [randomization] assuming 20% dropout by T2), we will have $>90\%$ power to detect a factor main effect or factor interaction effect of 2 units on the PHQ-9 scale.

By targeting 240 randomized participants, we will have ample power to detect factor main and interaction effects even with deviations from our assumptions (e.g., higher dropout rate, misspecified covariance matrix, etc.). For Aims 3 and 4, these samples should be adequate for theme saturation.

10. Subject Participation Duration

Participating subjects in aims 1, 3 and 4 will be asked to participate in a singular study visit lasting 30-60 minutes. Participating subjects in aim 2 will be asked to participate for up to a total of 3 months. Participating in the factorial trial (aim 2) will require 1 month of daily, active participation in which the patient is practicing mMT daily and completing weekly check-ins. At the end of the 1 month (post T1 completion), the patient will be asked to complete T2 survey. Once the patient has completed the T2 survey, he/she is finished with active study participation for an additional 2 months at which time they will be asked to complete T3 survey.

11. Study Duration

We estimate that from the time the factorial experiment trial opens to enrollment during Month 9 of Year 1, it will require approximately 41 months to complete data collection (approximately 36 months for cumulative enrollment with 4-5 months to complete all long-term follow up; this time does not include start up and analyses) and 4-6 months to perform all final data analyses for all Aims.

12. Risk-Benefit Assessment

Potential risks

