### 2.3 *Sample size*

As described below, we need to have sufficient statistical power to detect main effects or interactions of at least 1.6 points on the PHQ-9—our decision-making benchmark. We calculated power for the test of a main effect or factor interaction in a constrained longitudinal model via simulation. Based on LIFT pilot data, the baseline standard deviation of PHQ-9 was assumed to be 5.3 and the covariance between time points ranged from 3.9 to 11.5 (**Table 1**). We examined a range of sample sizes at T2, from 120 participants up to 200 participants.

However, given our experience in a past psycho-behavioral intervention trial with nearly 40% dropout, we revised our target sample size to 240 total participants. By targeting 240 randomized participants, we will have ample power to detect factor main and interaction effects even with deviations from our assumptions (e.g., higher dropout rate, misspecified covariance matrix, etc.). We simulated 500 different datasets under several smaller effect sizes of PHQ-9 (**Table 2**). If our assumptions about dropout are correct, then we have 80% power to detect a main effect or interaction effect of 1.6 on the PHQ-9 scale. Appendix B displays the Stata code for simulating power.

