## 6.2 Appendix B

### Stata code for simulation of power

```
/* Program to simulate data */
program powersimu, rclass
    version 16.0
    syntax, b1(real) [alpha(real 0.05)]

    clear
    set obs 192
    gen id = _n in 1/192

    *correlation matrix; estimates from PHQ-9 data from LIFT1 trial
    matrix V = (27.95, 9.67, 3.91 \ ///
                 9.67, 19.28, 11.54 \ ///
                 3.91, 11.54, 11.78)
    matrix list V
    matrix M = (0 \ 0 \ 0)

    *random effect drawn from a multivariate normal distribution
    drawnorm e1 e2 e3, means(M) cov(V)

    *check that the covariances line up with expected
    correlate e1-e3, covariance

    *set the 8 different intervention versions
    gen condition=1 in 1/24
    replace condition=2 in 25/48
    replace condition=3 in 49/72
    replace condition=4 in 73/96
    replace condition=5 in 97/120
    replace condition=6 in 121/144
    replace condition=7 in 145/168
    replace condition=8 in 169/192

    *set up the effect coded intervention components
    gen dose=1 if inlist(condition,1,2,3,4)
    replace dose=-1 if inlist(condition,5,6,7,8)

    gen symptoms = 1 if inlist(condition,1,2,5,6)
    replace symptoms = -1 if inlist(condition,3,4,7,8)

    gen call = 1 if inlist(condition,1,3,5,7)
    replace call = -1 if inlist(condition,2,4,6,8)

    *reshape to long format for fitting the statistical model
    reshape long e, i(id) j(time)

    *dummy code time
    replace time = time-1
    gen time1 = 1 if time == 1
    gen time2 = 1 if time == 2
    replace time1 = 0 if time1 != 1
    replace time2 = 0 if time2 != 1

    *rename variables for easier coding
    rename (dose symptoms call) (d s c)
    *note that t2 is the primary time point
    rename (time1 time2) (t2 t3)

    *generate interactions ahead of time
    gen ds = d*s
    gen dc = d*c
    gen sc = s*c
    gen dsc = d*s*c

    foreach x in t2 t3 {
        gen d`x' = d*x'
        gen s`x' = s*x'
        gen c`x' = c*x'
        gen ds`x' = d*s*x'
        gen dc`x' = d*c*x'
        gen sc`x' = s*c*x'
        gen dsc`x' = d*s*c*x'
    }

    *generate PHQ-9 with a main effect on dose at t2. All other effects are null.
    gen phq9 = 13+`b1'*dt2+0*st2+0*ct2+0*dct2+0*sct2+0*dsct2+0*dt3+0*st3+0*ct3+0*dst3+ ///
```

```

0*dct3+0*sct3+0*dsct3+e

*run mixed model with unstructured covariance on the residuals
mixed phq9 t2 t3 dt2 st2 ct2 dst2 dct2 sct2 dsct2 dt3 st3 ct3 dst3 dct3 sct3 dsct3 ///

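### Protocol 9 quotes its power for p<0.05 at a true 2-point effect but screens components on the estimate reaching 2 points; the SAP uses a different rule, and its retention and default clauses conflict

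*Protocol*

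**What the plan says.** Protocol 9 (Statistical Design and Analyses Plan, Aim 2) takes the estimated model coefficients and says "we will first determine if any of the main effects indicate improvement of at least 2 points on the PHQ-9 at T2". Components that fall short are set to the low level. The paragraph gives no p-value criterion.

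Protocol 9 (Sample Size and Power) describes a simulation under the alternative, "with power calculated as the proportion of times the estimated coefficient was found to be statistically significant at" p<0.05. It reports that "with 192 total patients at T2 (24 per experimental condition; 240 total at T1 [randomization] assuming 20% dropout by T2") the trial has more than 90% "power to detect a factor main effect or factor interaction effect of 2 units on the PHQ-9 scale".

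SAP 2.3 asks for "sufficient statistical power to detect main effects or interactions of at least 1.6 points on the PHQ-9—our decision-making benchmark", and Table 2 gives 79.8% power at 1.6 points. SAP 1.1 includes the comparator level when the main effect is 1.6 units or more, or p<0.05. SAP 4 repeats this as its retention clause, provided no interaction reaches the benchmark. It explains that the threshold came down from 2 to 1.6 units because a larger sample brought more power. SAP 4 then gives a default clause: the default level is kept when the difference is below 1.6 units or p exceeds 0.05.

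**The concern.** Power for a significance test and the chance that an estimate clears a fixed threshold are different quantities. When the threshold equals the assumed true effect, an unbiased, symmetrically distributed estimate falls short half the time, and a larger sample does not change that. The Protocol's power figure therefore does not describe the Protocol's screen.

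The SAP carries the same ambiguity. It treats 1.6 points both as the effect to be detected at p<0.05 and as a cut-off on the estimate. It also joins the two criteria with 'or' in the retention clause and again in the default clause. The complement of 'A or B' is 'neither A nor B', so the two clauses disagree whenever exactly one criterion is met.

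Selecting components is the purpose of Aim 2. The chance of keeping a useful component is the property a reader needs, and at present it depends on which sentence is followed.

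**Working it through.** **Inputs**
- Protocol 9 gives only a summary: "the baseline standard deviation of PHQ-9 was assumed to be 5.3 and the covariance between time points ranged from 3.9 to 11.5". SAP Appendix B gives the full matrix. Its first row, "matrix V = (27.95, 9.67, 3.91", supplies the T1 variance (27.95) and the T1–T2 covariance (9.67). Its second row, "9.67, 19.28, 11.54", supplies the T2 variance (19.28).
- 192 patients at T2, 24 in each of 8 conditions, so 96 against 96 for each factor.
- Two-sided alpha of 0.05.
- Effect coding, so an effect is twice its coefficient (note to SAP Table 2).

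**Standard error.** The constrained longitudinal model in effect adjusts T2 for T1:
- Var(T2 | T1) = 19.28 − 9.67²/27.95 = 15.93
- SE(effect) = 2 × √(15.93/192) = 0.576 points

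**The plan's own figures**
- Power at 2.0 points: Φ(2/0.576 − 1.96) = 93.5%, consistent with the Protocol's figure of more than 90%.
- Power at 1.6 points: Φ(1.6/0.576 − 1.96) = 79.3%, against 79.8% in Table 2.

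Both stated figures are right for the test at p<0.05.

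**Smallest estimate with p<0.05**
- N = 192: 1.96 × 0.576 = 1.13 points. An estimate of 1.6 has z = 1.6/0.576 = 2.78, so p = 0.0055.
- N = 144 (40% dropout from 240): SE = 2 × √(15.93/144) = 0.665, and 1.96 × 0.665 = 1.30 points.
- The cut-off reaches 1.6 only when N falls to 4 × 15.93 × (1.96/1.6)² ≈ 96.

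**Chance of meeting each rule.** For a threshold c on the estimate, this is 1 − Φ((c − true effect)/SE).

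| First-step rule for a main effect (N = 192) | True 1.6 | True 2.0 |
|---|---|---|
| p<0.05 (the test that was powered) | 79.3% | 93.5% |
| Protocol 9: estimate of 2 or more | 24.4% | 50.0% |
| SAP 1.1 and 4, retention clause: 1.6 or more, or p<0.05 | 79.3% | 93.5% |
| SAP 4, default clause read literally: 1.6 or more, and p<0.05 | 50.0% | 75.6% |

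The first and third rows agree because at this size every estimate of 1.6 or more already has p<0.05. In the fourth row the 1.6 threshold does the deciding, for the same reason.

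**True effect needed to pass the Protocol screen**
- 80% of the time: 2 + 0.8416 × 0.576 = 2.48 points
- 90% of the time: 2 + 1.2816 × 0.576 = 2.74 points

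**Simulation check.** I simulated 20,000 datasets with 24 patients per condition, all interactions in the model and T2 adjusted for T1. At a true 2 points, 93.4% had p<0.05, 49.5% had an estimate of 2 or more, and 74.8% had an estimate of 1.6 or more.

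**The case against.** The strongest reply is that the SAP has overtaken the Protocol rule. It was revised in 2022 and 2023, lowered the benchmark to 1.6 and added p<0.05 as an alternative route. Under that retention clause a true 2-point component is kept 93.5% of the time, in line with the Protocol's power statement. This stands, and it limits the 50% figure to the Protocol's own screen. It does not remove the difference between the two documents, or the SAP's contradictory default clause.

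A second reply is that the main-effect screen is only one step. Protocol 9 goes on to interactions, T3, secondary outcomes, feasibility and adherence, and SAP 4 also allows reconsideration. This stands too, although Protocol 9 applies the 2-point bar again to its final set.

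A reader might infer more than the documents support:
- *The trial will keep a truly useful component only half the time.* The SAP retention rule and the later steps do not support this.
- *The SAP's real cut-off is 1.13 points and 1.6 never matters.* That holds for main effects under the retention clause, at the planned size and with the pilot covariance. Under the literal default clause 1.6 does decide. The 1.13 also moves with the sample size, to about 1.30 at N = 144.
- *1.6 should no longer be called a benchmark.* SAP 1.1 and 4 rely on it to define an interaction large enough to change a decision.

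**Conclusion.** The point holds in a limited form. Within Protocol 9, the stated power of more than 90% does not describe the stated screen, which a true 2-point effect passes 50% of the time. Across the two documents, first-step retention of a true 2-point component is 50%, 75.6% or 93.5%, depending on which clause is followed. Within SAP 4, the outcome is undetermined for an estimate between about 1.13 and 1.6 points. Such an estimate meets the retention clause through p<0.05 and the default clause through its size.

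The power calculations themselves are sound for p<0.05. The figures assume the pilot covariance matrix, an approximately normal unbiased estimate, 192 evaluable patients balanced over the conditions, and null interactions. They are probabilities for the first step, not for the final package.

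**What to change.** State one main-effect rule in the same words in Protocol 9 and SAP 1.1 and 4, and attach the probability that belongs to it.

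- **If the rule is 1.6 points or more, or p<0.05, in the beneficial direction:** rewrite the SAP 4 default clause as the complement (below 1.6 points and p of 0.05 or more). Replace the 2-point screen in Protocol 9. Table 2 can stay as it is. Add a sentence that p<0.05 is the operative criterion for main effects at the planned size.
- **If the rule is a threshold on the estimate, or both criteria together:** restate the figures in Protocol 9 and Table 2 as the probability of meeting that rule. Requiring both 1.6 points and p<0.05 gives 50% at a true 1.6 points and 75.6% at 2. Requiring an estimate of 2 points gives 50% at a true 2 points and 80% at about 2.48.

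In either case keep 1.6 as the interaction benchmark. The cost is wording in both documents, a revised Table 2 only under the second option, and possibly a less favourable stated figure. No new data are needed.

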For aims 1, 3 and 4 each participant will be asked to complete a singular study visit that will last approximately 30-60 minutes. During this study visit, post consent, the individual may be asked to do the following:

- Find and install the Pattern Health app (aim 1 and aim 4)
- Register to the LIFT2 study (aim 1 and aim 4)
- Complete baseline survey (aim 1 and aim 4)
- Randomize to 1 of 3 groups or screen fail purposely (aim 1 and aim 4)
- Audio-recording for interview using qualitative analyses (aim 3)
- Provide feedback on app content and usability (aim 1, 3, and 4)

For aim 2, each consented patient will be asked to complete up to four individual study visits.

- **Baseline:** this visit is to occur post-consent (same day, ideally) at the time of hospital admission just prior to discharge. However, this visit may occur at the time of hospital discharge within 7 days of returning to home. At this visit, the following will occur:
 - App Registration
 - Baseline Survey Completion
- **T1 (Day 0) (+30 days):** this visit is to occur at the time of hospital discharge to home, ideally within the first week (7 days) of returning to home; however, it can occur up to 1 month (30 days) from the time of hospital discharge to home. At this visit, the patient will complete the T1 survey via the app, which includes the PHQ-9, PTSS, PHQ-10, and MAAS surveys. Score dependent, the patient will be randomized to 1 of 8 intervention combinations. If the patient's psychological distress score is too low; he/she will receive an automated alert via the app describing they are not eligible and their study participation is complete.
- **T2 (Day 30) (+60 days):** this visit is to occur post 1 month randomization for those patients who remain eligible to participate in the study. PHQ-9, PTSS, PHQ-10, and MAAS surveys will be administered again. If the patient's survey scores indicate high levels of distress, as defined by a triggered SI alert or increased distress score from T1, a delegated study team member will contact the patient for safety precautions.
- **T3 (Day 90) (+30 days):** this visit is to occur post 3 months randomization for those patients who remain eligible to participate in the study. PHQ-9, PTSS, PHQ-10, and MAAS surveys will

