Appendix 1: Schedule of Events

	Day 0 (In-Hospital, Baseline)	Day 1 , T1 (Discharge) (+30 days)	Week 1	Week 2	Week 3	Week 4 Day 30, T2 (+60 days)	Day 90 (+30 days), T3
Screening*	X						
Consent (a)*	X						
App Registration*	X						
Baseline Survey (b)*	X						
Usability Survey*							
T1 Survey (c)		X					
T2 Survey (c)						X	
T3 Survey (c)							X
Weekly Check-In (d)			X	X	X		
Data Entry (e)	X	X				X	X
AE/SAE assessment (f)	X	X				X	X
Survival Status (f)		X				X	X
End of Study (g)							X

- a) Patients may be approached and consented during their admission, if well enough; their hospitalization (e.g., while in step-down), or within 7 days of returning to their home for participation in the study.
- b) Completion of the baseline survey includes the patient providing self-reported information such as social and demographic information and general health status.
- c) Surveys 1, 2 and 3 will be completed via the app by all study participants, regardless of intervention combination assignments.
- d) For those participants randomized to 1 of the 8 intervention combinations, they will complete a weekly check-in to ascertain overall safety of the patient and usefulness of coping skills practice.
- e) AE/SAE assessment and survival status will be completed via EMR review and/or telephone interview.
- f) Study completion for patients enrolled in the study is considered to occur at the completion of T3. However, participants may undergo EOS if they are withdrawn from the study by the PI or opt to withdraw from the study voluntarily at any time. Should withdraw of a patient occur, the reason for withdraw and date of withdraw will be documented. AE/SAEs and survival status will be noted, as applicable.

*For aim 1 only.

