## 2.6 Data Decisions

Per the protocol, all participants with measures out of window will be removed from the analysis. The windows are as follows:

Time Point	Window
1 month post-randomization (T2)	Up to 60 days post-randomization (+30 days from 1 month)
3 months post-randomization (T2)	Up to 120 days post-randomization (+120 days from 3 months)

Records outside of that window are identified in the final dataset using an indicator called “outofwindow”.

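### The exclusion windows in SAP 2.6 give T3 two limits (day 120 and day 210) under a T2 label, and remove primary-outcome surveys on days 61-90 that the protocol counts as in window

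*Protocol*

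**What the plan says.** **SAP.** Section 1 counts T2 and T3 from randomization, at 1 and 3 months. Section 2.6 removes measures outside the window from the analysis, says that this follows the protocol, and marks the affected records with a flag named outofwindow. Its 1-month row allows up to day 60 after randomization, explained as 30 days beyond 1 month. Its 3-month row carries the label T2 and reads "Up to 120 days post-randomization (+120 days from 3 months". SAP 3.1 makes PHQ-9 at T2 the primary outcome. SAP 3.2 lists the T3 measures as secondary, and SAP 4 allows T3 to prompt reconsideration of the components kept.

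**Protocol Section 7, Study Visits.** T1 is Day 0. For T2, "this visit is to occur post 1 month randomization for those patients who remain eligible to participate in the study", with the heading "T2 (Day 30) (+60 days". For T3, "this visit is to occur post 3 months randomization", with the heading "T3 (Day 90) (+30 days".

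**Protocol Section 10.** T2 is requested 1 month after T1 is completed. After T2, the patient "he/she is finished with active study participation for an additional 2 months at which time they will be asked to complete T3 survey". The same section limits Aim 2 participation to a total of 3 months.

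**Protocol Appendix 1.** Day 0 is the in-hospital baseline and the next column is "Day 1 , T1 (Discharge) (+30 days". T2 and T3 stay at Day 30 (+60 days) and Day 90 (+30 days).

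**The concern.** A window table that decides which data are dropped has to yield one limit per visit, and it has to match the document it claims to follow. This one fails on both counts.

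- A programmer coding the flag for the 3-month row could use day 120 or day 210 and would obtain different T3 datasets.
- For T2, sites working to the protocol may collect a survey as late as day 90 in good faith, and the SAP then discards anything after day 60. That is the primary outcome, in an analysis that SAP 4 calls intention-to-treat.

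Late surveys are not a remote case. Protocol Section 12 expects most patients to miss their visit windows and does not treat this as a deviation. The Section 10 and Appendix 1 wording adds doubt about the date from which a window is counted.

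**Working it through.** **1. Window arithmetic.** Formula: limit = nominal day + allowance, with 1 month = 30 days.

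| Visit | Source | Calculation | Last day in window |
|---|---|---|---|
| T2 | SAP 2.6 | 30 + 30 | 60 (agrees with its own text) |
| T2 | Protocol Section 7 and Appendix 1 | 30 + 60 | 90 |
| T3 | SAP 2.6, first clause | stated | 120 |
| T3 | SAP 2.6, parenthesis | 90 + 120 | 210 |
| T3 | Protocol Section 7 and Appendix 1 | 90 + 30 | 120 |

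The SAP's T2 row reproduces from its own parts; its T3 row does not. The two T3 limits differ by 210 - 120 = 90 days. The two T2 limits differ by 90 - 60 = 30 days.

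**2. Surveys treated differently by different passages.**
- T2 on days 61-90: kept by the protocol window, removed by the SAP.
- T3 on days 121-210: kept by the SAP's parenthesis, removed by the SAP's first clause and outside the protocol window.

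**3. Section 10 read as T3 = T2 completion + 60 days.**
- T2 on day 30: T3 on day 90.
- T2 on day 60: T3 on day 120, still inside the limit.
- T2 on day 61: T3 on day 121, outside.
- T2 on day 90: T3 on day 150, outside.

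On this reading the wording moves T3 past day 120 only when T2 falls on days 61-90.

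**4. Starting events.** SAP 2.4 allocates patients when T1 is completed, so T1 completion and randomization are the same moment. Section 7, Section 10 and the SAP therefore agree on the start of the T2 clock. Appendix 1 differs in calling T1 Day 1.

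**5. What T2 removals could cost in power (illustration).** The inputs are the covariance matrix in SAP Appendix B, 192 analysed participants (96 per factor level), a difference of 1.6 and two-sided alpha of 0.05 (sidedness is my assumption).
- SD of T2 given T1 = sqrt(19.28 - 9.67²/27.95) = sqrt(15.93) = 3.99.
- SE = 3.99 × sqrt(2/96) = 0.576.
- 1.6/0.576 = 2.78, and power = Φ(2.78 - 1.96) = 79.3%. SAP Table 2 gives 79.8%, so the plan's figure reproduces.

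The share of T2 surveys on days 61-90 is not in the documents. If a further 5%, 10%, 20% or 30% of the 192 were removed, spread evenly over the factor levels, power would be about 77%, 75%, 70% or 64%.

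**The case against.** The strongest reply is that these are slips. The SAP's first clause says day 120, the protocol says 90 + 30 = 120, and the SAP's T2 row is built the same way, so +120 is very probably meant as +30 and the T2 label as T3. I accept that as the likely explanation. It does not remove the need to correct a cell that defines an exclusion. Nor does it explain the T2 row, which is coherent in itself and still contradicts the protocol by 30 days. A sponsor may choose a narrower analysis window than the visit window, but the SAP does not say that it has done so; it says that it follows the protocol.

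A reader might also infer more than the documents support:

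- *Three rival clocks for both visits.* T2 does not have three, because T1 completion is randomization. The most that can be said is that T3 has a loosely worded alternative and Appendix 1 a different day label.
- *Section 10 instructs sites to schedule T3 out of window.* One month plus 2 further months is that section's own 3-month total, and a T3 on days 121-150 would break that cap. The wording is loose, not a firm competing schedule. Even taken literally, it affects only patients whose T2 is already past the SAP's day 60. If removal is by participant, as the SAP's rule literally says, they are already out; if by record, as its flag suggests, their T3 would be lost as well.
- *Appendix 1 puts T2 before the programme is delivered.* Counting Day 30 from the in-hospital baseline with a 30-day lag to T1 would give that result. But the table's own columns run T1, Weeks 1 to 3, then Week 4 with T2, so T2 follows the programme. What remains is a Day 0/Day 1 mismatch.
- *The 75% retention benchmark is altered.* Protocol Section 4 does not tie that benchmark to these windows.

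**Conclusion.** The point holds for the SAP's exclusion windows. The T3 row is mislabelled and gives two limits 90 days apart, of which only day 120 matches the protocol. The T2 limit is day 60 in the SAP and day 90 in the protocol, so a primary-outcome survey on days 61-90 is acceptable under one and removed under the other. The T2 conflict is the more important, because it bears on the primary outcome and cannot be dismissed as a typing error. The documents do not show which T2 limit was intended.

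The Section 10 wording and the Appendix 1 day labels are secondary points of clarity. The day counts take 1 month as 30 days. The number of surveys affected is unknown, and the power figures show only what would follow from assumed shares.

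**What to change.** 1. In SAP 2.6, relabel the 3-month row T3 and change its parenthesis to +30 days, leaving the limit at day 120. Do not add a lower bound; the SAP has none.
2. Reconcile the T2 limit between SAP 2.6 and Protocol Section 7 and Appendix 1 before the outofwindow flag is applied. If the SAP is meant to be narrower than the visit window, it should say so and no longer attribute the limit to the protocol.
3. Compute the flag from the randomization date, and state whether it removes the record or the participant.
4. In Protocol Section 10, state that T3 is due 3 months after randomization whatever the date of T2.
5. In Appendix 1, relabel the columns so that T1/randomization is Day 0 and the in-hospital baseline precedes it.

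The cost is wording in the two documents plus one check of the flag code and the app's survey-release dates. No visits or assessments are added.
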